## **LIST OF ABBREVIATIONS**

APPS : Applications

AROM : Active Range of Motion

BMI : Body Mass Index

ROM : Range OF Motion

UG : Universal Goniometer

# CHAPTER I

## INTRODUCTION

Range of motion (ROM) of the joint is one of the factors that determine function of the musculoskeletal system. This parameter should be measured and recorded by a valid and reliable method (**Yaikwawongs et al., 2009**). It is considered to be an essential component of lower limb physical examination, which can be applied using various instruments such as goniometers and inclinometers (**Pourahmadi et al., 2017**).

Range of motion of the knee joint is one of the major factors determining the outcome after knee injuries. It is also an important measurement required by many knee scoring systems to determine the preoperative status and postoperative outcome (**Anouchi et al., 1996**). Measurements are used by physical therapists to quantify limitations of motion, used to decide an appropriate therapeutic interventions, and document the effectiveness of these interventions. The ideal measuring device should give reproducible valid and reliable data (**Yaikwawongs et al., 2009**).

Two-arm digital goniometer is still widely used in measuring uniaxial ROM of joint of extremity, there is high validity, intra rater and interrater reliability of the digital goniometer. It is considered valid and reliable tool that simplify physical therapists' work (**Svensson et al., 2019**).

The measurement of joint ROM is required an essential skill in the musculoskeletal assessments commonly performed by physiotherapists. The digital goniometer is the most commonly utilized clinical tool for measuring joint range of motion, the evolution of sensors technology and applications are easy to use, relatively inexpensive, and highly accessible (**Keogh et al., 2019**).

Rebee is a wearable motion sensor package of sensor with its own mobile application, which measures range of joint movement in different planes easily which the patient able to wear the sensor and move easily to measure ROM and record the measurement at the application software, that is facilitate the tele-measurement which the patients are supposed to put on the sensors and perform the actions themselves, or with assistance from physical therapist.

So this study will be conducted to test the criterion related validity and intrarater reliability of the rebee wearable sensor in measuring active knee joint ROM compared with digital goniometer measurement.

### **Statement of the Problem**

- 1- Is the rebee wearable sensor valid to measure active knee joint ROM compared with digital goniometer measurement?
- 2- Is the rebee wearable sensor reliable in measuring active knee joint ROM?

### **Purpose of the Study**

Purpose of the study to test the criterion related validity and intrarater reliability of rebee wearable sensor in measuring active knee joint ROM compared with digital goniometer measurement.

### **Significance of the Study**

Measurement the joint ROM with the digital goniometer is considered time consuming and difficult with respect to repeated measurements. (**Svensson et al., 2019**).

So there is a need to the sensors system which could be considered as a clinical measurement for ROM which will reflect in rehabilitation process through measuring the patient ROM easily (**Hamel et al., 2008**).

Some researchers would prefer taking the ROM of lower limb in a more functional way such as standing and walking given that the sensors were

developed, which the patients are supposed to put on the sensors where the sensor placed on prominent bony landmarks at the level of lateral malleolus. It will be stabilized on the testing limbs by elastic bands and perform the actions themselves, with or without the supervision from the physical therapist (Vohralik et al., 2015).

With the use of rebee wearable sensor, the ROM of knee joint flexion and extension can be monitored easily and recorded, that lead to facilitation of tele rehabilitation. Which the patients are supposed to put on the sensors and perform knee flexion and extension themselves, with or without the supervision from the clinicians.

## **Hypotheses**

It is hypothesized that:

1. Rebee wearable sensor will not be valid to measure active knee joint flexion ROM compared with digital goniometer measurement.
2. Rebee wearable sensor will not be valid to measure active knee joint extension ROM compared with digital goniometer measurement.
3. Rebee wearable sensor is not reliable to measure active knee joint flexion ROM.
4. Rebee wearable sensor is not reliable to measure active knee joint extension ROM.

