## Instrumentations

1. Digital goniometer.

The digital goniometer will be used as a valid and reliable ROM measurement tool, the type of digital goniometer will be used in the study called digital absolute axis goniometer with accuracy about 0.99(**Correll et al., 2018**)

2. Rebee wearable sensor and application by XCLR8 Technologies.

The package of sensor and application will be used for measure, interpret and store participant measurement for test the criterion related validity and intrarater reliability of rebee wearable sensor in measuring active knee joint ROM

3. Health weight scale for weight and height measurement to calculate BMI. (BMI= weight (kg) / [height (m)]) (**Weisell et al., 2002**).

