## Measure AROM of Knee Flexion with Digital Goniometer

The participant will be at supine position with the testing knee extended, which allows assessment of the joint ROM without interference from tightness in the rectus femoris muscle, axis location at lateral epicondyle of the femur, stationary arm will be along the femur to the greater trochanter, The movement arm will be along the fibula to lateral malleolus.

[figure not shown]
The participant will be asked to flex the testing knee fully through available ROM and the therapist will record the measurement to compare with rebee wearable sensor measurement.

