## Measure AROM of Knee Extension with Digital Goniometer

The participant will be at supine position with the testing knee flexed, which allows assessment of the joint ROM without interference from tightness in the rectus femoris muscle, axis location at lateral epicondyle of the femur, stationary arm will be along the femur to the greater trochanter, The movement arm will be along the fibula to lateral malleolus.

The participant will be asked to extend the testing knee fully through available ROM and the therapist will record the measurement to compare with rebebe wearable sensor measurement.

The following picture illustrates that measurement with the digital goniometer will be from the similar supine position of measurement with the conventional goniometer.

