## Procedure for testing Reliability

Designed according to Guidelines for reporting Reliability and Studies, investigating the intrarater reliability of a rebebe wearable sensor will be conducted. The study will be designed in accordance with the ethical guidelines from the Helsinki declaration of ethical principles (World Medical Association (Kottner et al., 2011)).

Written consent will be retrieved from all subjects before participating in the study, the procedures will be repeated two times with one week interval between measurements. Researcher will record all the measurement.

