### **Measure AROM of Knee Flexion with Rebee Wearable Sensor**

The participant will be standing in upright position, the sensor position at the level of the Lateral malleolus, participant will be asked to flex the testing knee fully while standing supported in one leg.

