## **Statistical Analysis**

Statistical methods will be used to calculate the reliability and validity of our measurements will be descriptive statistics for mean and standard deviation, also the Pearson product-moment correlation coefficient (r), an assessment of covariance.

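### 'Valid' and 'reliable' are given no numerical meaning, and Pearson's r, the only planned statistic relating the paired readings, cannot show agreement

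*Combined protocol and SAP*

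**What the plan says.** The combined protocol and SAP has four hypotheses (Chapter I, Hypotheses). The validity hypothesis for flexion is "Rebee wearable sensor will not be valid to measure active knee joint flexion ROM compared with digital goniometer measurement"; the reliability hypothesis is "Rebee wearable sensor is not reliable to measure active knee joint flexion ROM". Extension has the same wording in each case. None names a parameter, a margin or a cut-off.

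The Statistical Analysis section is one sentence. It covers validity and reliability together, with "descriptive statistics for mean and standard deviation, also the Pearson product-moment correlation coefficient (r), an assessment of covariance".

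Two other places might be thought to supply a criterion, and neither does:

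- Procedure for testing Reliability says "Designed according to Guidelines for reporting Reliability and Studies", but names no statistic or threshold.
- Instrumentations describes a "digital absolute axis goniometer with accuracy about 0.99". That figure concerns the reference goniometer, has no unit and sets no limit for the sensor.

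Participants and Delimitations give a sample of 40 from G*Power, without inputs.

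**The concern.** Validity against a reference and test-retest reliability both turn on how far apart two readings on the same person are. Pearson's r measures only how closely the pairs follow some straight line with positive slope. It is unaffected by a constant offset, by a scale difference between devices, or by a shift between the two weekly sessions. Separate means might reveal an average offset, but the plan has no rule for judging one. Nothing planned measures the within-person spread of differences in degrees.

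Two things are at stake. A sensor that reads consistently high or low could be called valid, and one that drifts from week to week could be called reliable. And with no benchmark, the meaning of both words can be chosen after r is known. The Introduction says ROM readings are used to quantify limitation and to choose interventions, so an error in degrees matters even when correlation is high.

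An offset is plausible here. The goniometer is read supine for both movements (flexion: "The participant will be at supine position with the testing knee extended"; extension: "The participant will be at supine position with the testing knee flexed"). The sensor is read upright for flexion ("The participant will be standing in upright position") and seated for extension.

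**Working it through.** **Does the sample size imply a hidden criterion?** It cannot be reproduced, because no alpha, power, effect size or test is stated. Several unrelated inputs give about 40:

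- Correlation against zero, n = ((z_alpha + z_power)/atanh r)² + 3, two-sided 0.05: r of about 0.43 at 80% power, or 0.49 at 90%.
- r0 = 0.6 against r1 = 0.8, one-sided 0.05, 80% power: 41.
- Paired standardised difference of 0.45, two-sided 0.05, 80% power: (2.80/0.45)² gives 39.

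So 40 points to no particular criterion.

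**Inputs for the illustration.** All are assumed, since the documents give none: r = 0.95; equal SDs of 5, 7 or 9 degrees; device offset 5 degrees; session shift 3 degrees.

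**Formulas.** With offset or shift d:

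- Absolute-agreement ICC = r·SD² / (SD² + d²/2)
- SD of differences = SD·√(2(1 − r))
- Limits of agreement = d ± 1.96 × SD of differences

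| SD | r | ICC, d = 5 | SD of differences | Limits, d = 5 | ICC, d = 3 |
|---|---|---|---|---|---|
| 5 | 0.95 | 23.75/37.5 = 0.63 | 1.58 | 1.9 to 8.1 | 23.75/29.5 = 0.81 |
| 7 | 0.95 | 46.55/61.5 = 0.76 | 2.21 | 0.7 to 9.3 | 46.55/53.5 = 0.87 |
| 9 | 0.95 | 76.95/93.5 = 0.82 | 2.85 | −0.6 to 10.6 | 76.95/85.5 = 0.90 |

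r is the same in every row, whatever d is.

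**How weak could the criterion be?** If r were merely tested against zero (assumed; two-sided 0.05), the critical value at n = 40 is t/√(38 + t²) = 0.312. An observed r of 0.32, with 95% CI 0.01 to 0.57, would then reject 'not valid'.

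**What 40 delivers for agreement, one pair per participant:**

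- Mean difference, 95% CI half-width: t/√40 = 0.32 SD of the differences.
- Each limit of agreement: t·√(1/40 + 1.96²/(2·39)) = 0.55 SD of the differences.
- Standard error of measurement (SEM) = SD of differences/√2, and minimal detectable change (MDC) = 1.96·√2·SEM. Both have 95% CI factors √(39/χ²) of 0.82 to 1.28.
- Chance that the lower 95% bound of the ICC exceeds an illustrative 0.75 (simulation, 40,000 runs per case, no systematic shift): 87% at true ICC 0.90, 41% at 0.85. With 36 returning at one week (assumed), 83% and 37%.
- At a consistency ICC of 0.90, a session shift of 0.1, 0.2 or 0.3 total SD lowers the 87% to 80%, 50% or 13%.

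**Dependence on sample spread.** Take an assumed within-person error SD of 2 degrees, so MDC = 1.96·√2·2 = 5.5 degrees throughout. ICC = B²/(B² + 4), where B is the between-person SD:

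| B (degrees) | ICC | Chance of clearing 0.75 |
|---|---|---|
| 3 | 0.69 | under 1% |
| 4 | 0.80 | 11% |
| 5 | 0.86 | 52% |
| 6 | 0.90 | 87% |

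The expected r follows the same formula, so r shares this weakness.

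**The case against.** The stated aim is criterion-related validity, not interchangeability. Correlation with a reference measure is a recognised part of that, and the plan never claims to show agreement. This stands in part: a high r would support linear association. It does not supply the missing decision rule, and it fails for reliability, where a shift between sessions is itself the error of interest.

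Limits of agreement would not give a clean verdict on the device either, because posture differs between the two devices. A failed margin could be due to posture, and a pass could hide opposite effects that cancel. This stands as a limit on what may be concluded. Using r does not remove the confound; it only keeps any resulting offset out of sight.

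The sizes shown rest on assumed SDs and offsets, and at SD 7 or 9 a 5-degree offset still leaves the point ICC above 0.75. The test against zero is likewise only one possible reading of the plan. Both are correct. The invariance of r and the absence of a criterion do not depend on those inputs.

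The 87% is a best case. It assumes no session shift and applies to one movement; if flexion and extension were independent (assumed), clearing both would be about 0.87² = 75%. SEM from the SD of differences also ignores a systematic shift, so the between-session mean difference must be read beside it. These points belong in the restated plan.

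**Conclusion.** The concern holds. The documents give no numerical definition of valid or reliable, and the one planned statistic that links the paired readings cannot detect a constant device offset, a scale difference or a session shift. Followed as written, the plan could support calling a biased sensor valid or a drifting one reliable. This is a wrong choice of analysis for both stated purposes, not merely missing detail.

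Those conclusions follow from the text and from the algebra of r. The sizes are illustrations under assumed inputs: at r = 0.95, a 5-degree offset corresponds to an ICC between 0.63 and 0.82, and a 3-degree session shift to an ICC between 0.81 and 0.90, over SDs of 5 to 9 degrees.

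**What to change.** Before data are seen, and for flexion and extension separately:

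1. **Validity.** Base the conclusion on the mean paired difference and the 95% limits of agreement, each with 95% CIs in degrees, against a margin that the investigators fix and justify. Say whether the limits themselves or their outer confidence bounds must lie inside it. Report the ICC as support. State that the difference combines device and posture, so neither a pass nor a failure can be attributed to the sensor alone.
2. **Reliability.** Report the absolute-agreement ICC with its lower 95% bound against a justified benchmark (0.75 is used here only as an illustration), together with the between-session mean difference, SEM and MDC in degrees. State how a between-session mean difference will be judged. The sample is narrow (age 35 to 45, BMI 19 to 25), so also say in advance how a low ICC with a small MDC will be read.
3. **Pearson's r and sample size.** Keep r as descriptive. Keep 40, and state the precision it gives: 0.32 SD of the differences for the mean difference, 0.55 SD for each limit, and a factor of 0.82 to 1.28 for SEM and MDC. Give the ICC pass rates with their conditions, including the effect of a session shift.

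The cost is wording in Hypotheses and Statistical Analysis, a sentence in Participants, and the work of justifying a margin and a benchmark. No new measurements are needed, though the posture confound remains. The downside is that the sensor becomes harder to pass, the study's stated strength looks less favourable, and an ICC benchmark used alone could fail the sensor simply because the participants are alike. That last risk is why the figures in degrees must accompany it.

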### **Participants**

40 normal participant will be assigned to one group, this number detected by G\*power 3.1 software (Universities, Dusseldorf, Germany) was used for calculation.

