### **Measure AROM of Knee Extension with Rebee Wearable Sensor**

The participant will be sitting at the edge of plinth with knee flexed, the sensor position at the level of the Lateral malleolus, participant will be asked to extend the testing knee through the full ROM.

[figure not shown]

The Digital goniometer and rebee wearable sensor will be used for comparison of their validity for measuring knee joint flexion and extension ROM.

Rebee wearable sensor will be used as mentioned above and this procedures will repeated two times with one week interval between measurements to test its reliability. Researcher will records all the measurement.

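### The four yes/no hypotheses on validity and reliability have no acceptance criterion, and Pearson r alone could not expose a systematic error of tens of degrees

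*Combined protocol and SAP*

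**What the plan says.** The Statement of the Problem asks two yes/no questions, one of which is "Is the rebee wearable sensor reliable in measuring active knee joint ROM". The Hypotheses section turns them into four null-type statements, for flexion and extension separately. Validity for flexion reads "Rebee wearable sensor will not be valid to measure active knee joint flexion ROM compared with digital goniometer measurement"; reliability for flexion reads "Rebee wearable sensor is not reliable to measure active knee joint flexion ROM". The extension statements follow the same pattern.

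Statistical Analysis is a single sentence covering both aims. It opens "Statistical methods will be used to calculate the reliability and validity of our measurements" and then names "descriptive statistics for mean and standard deviation" and "also the Pearson product-moment correlation coefficient (r), an assessment of covariance". It gives no test, alpha, confidence interval, agreement statistic or cut-off.

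The Participants section says "40 normal participant will be assigned to one group, this number detected by" G*Power, without effect size, alpha, power or test family. The sensor procedure adds "this procedures will repeated two times with one week interval between measurements to test its reliability". The only accuracy figure in the document, under Instrumentations, is about 0.99; it has no unit and concerns the goniometer.

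**The concern.** The study has to give four yes/no answers and has nothing to decide them by. Either the labels are chosen after the results are seen, or the usual default takes over and r is tested against zero. That default is a low bar for two measurements of knee motion in the same person. It also cannot see a constant or proportional error, because r does not change when one instrument is shifted or rescaled.

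The Introduction and the literature review say that range-of-motion readings serve to choose interventions, document their effect and monitor change. The Significance section adds unsupervised tele-rehabilitation. For those uses a clinician needs the error in degrees. A bare label of valid or reliable does not give it.

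**Working it through.** **Inputs.** From the documents: n = 40, two sessions one week apart, Pearson r. Assumed, because the documents give none: two-sided alpha 0.05, true between-person SD 6 degrees, goniometer error SD 2 (or 0 where stated), and sensor error SDs as shown. What matters is the ratio of error to true SD, so results in degrees scale with the assumed SD.

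**The plan's own figure.** The sample size of 40 cannot be reproduced without inputs. For a two-sided 5% test of zero correlation it would match r = 0.43, 0.49 or 0.53 at 80%, 90% or 95% power. It therefore does not reveal which rule was intended.

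**The bar under a test against zero.** Critical r = t/√(n − 2 + t²), with t = 2.024 on 38 df: 2.024/√(38 + 4.10) = 0.312, and r² = 0.097. At an observed r of 0.312 the 95% interval is 0.001 to 0.568. Other alphas move the bar little: 0.26 at one-sided 5%, 0.39 at two-sided 1.25%, 0.40 at two-sided 1%.

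**Rejection probability.** Approximately P(Z > [atanh(0.312) − atanh(ρ)] × √37), where atanh(0.312) = 0.323 and √37 = 6.083. Simulation agrees to within about one percentage point.

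**Systematic error (sensor error SD 3, goniometer error SD 2).**
- Constant 30-degree offset: validity ρ = 36/√(40 × 45) = 0.85 and retest ρ = 36/45 = 0.80. Both nulls are rejected in essentially 100% of studies. The offset appears in neither formula.
- Sensor reading 75% of the true angle (about −34 degrees at an assumed 135): validity ρ = 27/√(40 × 29.25) = 0.79 and retest ρ = 20.25/29.25 = 0.69. Rejection is 99.9% or more for both.
- Sensor shifting by 20 degrees between sessions, a failure of reliability itself: retest ρ stays at 0.80. An absolute-agreement ICC would be about 36/(36 + 200 + 9) = 0.15, where 200 = 20²/2 is the between-session variance.

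**Random error (error-free reference).** Validity ρ = 6/√(36 + e²) and retest ρ = 36/(36 + e²), where e is the sensor error SD. The retest value is lower because both readings carry sensor error.

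| e | 95% of readings within | Validity ρ, rejected | Retest ρ, rejected |
|---|---|---|---|
| 6 | ±12 | 0.71, about 100% | 0.50, about 92% |
| 10.4 | ±20 | 0.50, about 92% | 0.25, 34 to 35% |
| 20 | ±39 | 0.29, about 44% | 0.08, 7 to 8% |

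With goniometer error SD 2, the 92% for validity at e = 10.4 becomes 89%. At e = 6 the reliability null usually falls, yet the smallest detectable change is 1.96 × √2 × 6 = 16.6, about 17 degrees.

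**What 40 participants can support.**
- A lower 95% bound above 0.75 needs an observed coefficient of tanh(atanh(0.75) + 1.96/√37) = 0.86 (Fisher approximation).
- Each limit of agreement has a 95% half-width of about 0.55 SD of the differences: about 2 degrees if that SD is √(3² + 2²) = 3.6.
- With no mean difference, limits inside ±5 degrees need an SD of differences of at most 5/1.96 = 2.6. Putting the confidence bounds inside needs 5/(1.96 + 0.55) = 2.0. For ±10 the figures are 5.1 and 4.0.

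**The case against.** The plan states no significance test, so the test against zero is the reviewer's inference. That is correct. A reader might infer that any non-zero association rejects the nulls; the documents do not say so, and even the inferred test needs an observed r of about 0.31.

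A reader might also infer that a sensor with tens of degrees of error would in general be called both valid and reliable, or that the study is almost bound to reject all four nulls. The table contradicts both. At error SD 10.4 the reliability null survives in about two studies out of three, and at 20 in more than nine out of ten. The stronger reading holds for systematic error only.

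Nor does every coefficient share the weakness to the same degree. An absolute-agreement coefficient penalises a shift that Pearson r ignores, so the choice of coefficient is part of the problem.

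Two further points stand in part. Means are reported, so an offset would be visible, but nothing in the plan makes it count against the label. And a high validity r is not assured, because the instruments are read in different positions: goniometer supine, sensor standing for flexion and sitting for extension. This weakens any claim that validity is certain to pass. It also makes a systematic difference between instruments plausible, which is the kind that r misses.

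**Conclusion.** The point holds in this form. Four yes/no hypotheses have no acceptance criterion in degrees or as a coefficient, and no decision rule. This rests on the text alone. What follows depends on the inferred zero test and the assumed alpha and SDs: r of about 0.31 suffices, and a constant or proportional error of tens of degrees passes both tests in essentially every study. A constant offset present in both sessions is strictly a validity failure; the matching reliability failure, a shift between sessions, escapes as well. Moderate random error can also earn the reliable label (about 92% at error SD 6, with a smallest detectable change of about 17 degrees). Large random error usually does not. Replacing Pearson r without adding a criterion would still leave both labels undefined. The change should be made, because the study's conclusions are these labels.

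**What to change.** Before data collection, attach a criterion to each statement in Hypotheses and put the matching analysis in Statistical Analysis.

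- **Validity, per movement:** report the mean sensor-goniometer difference and 95% limits of agreement with confidence intervals. Judge them against a margin in degrees that the sponsor names and justifies (5 and 10 are used above only for illustration). State whether the limits or their confidence bounds must lie inside it.
- **Reliability, per movement:** require the lower 95% confidence bound of an absolute-agreement test-retest ICC to exceed a named value (0.75 for illustration). Report the standard error of measurement and the smallest detectable change in degrees, the latter judged against the same margin.
- **Label:** use valid or reliable for a movement only if its mark is met; otherwise report the size of the error without the label.
- **Position:** state that the validity difference includes any effect of the different test positions, or reconcile the goniometer and sensor measurement sections.

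The cost is protocol wording and a few lines of analysis, using the paired and repeated readings already planned. The downside is that a positive label becomes harder to earn. The sponsor should check the chosen marks against what 40 participants can support.
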